### 2.2 Secondary objective

To compare postoperative pain intensity (VAS score, 0-10) at postoperative days 1 and 3.

To compare length of hospital stay.

To compare the incidence of major postoperative complications within 30 days

To compare total operative times (minutes).

To compare total wound-related cost-effectiveness between the two groups, including device cost and wound dressing service cost.

To assess wound healing quality and patient satisfaction via a validated questionnaire administered at the outpatient clinic visit one week after discharge.

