### 3.4 Randomization

Randomization was performed using a computer-generated sequence created by the Department of Biostatistics at Seoul St. Mary's Hospital. Allocation was stratified by surgical approach (laparoscopic vs robotic-assisted) and tumor location (colon vs rectum). Within each stratum, block randomization with variable block sizes (4,6, and 8) ensured balance while minimizing predictability.

Allocation concealment was achieved through a centralized, web-based system managed by an independent biostatistician not involved in patient recruitment, enrollment, or outcomes assessment. Patients were randomized

the day before surgery in a 1:1 ratio to either the skin adhesive (Bond) or skin stapling (Stapler) group. Treatment allocation was concealed from all clinical staff until assignment.

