#### **3.6.2 Secondary Endpoints**

Outcomes	Measurement Tool	Time point
Pain score	Visual Analogue Scale (VAS, 0-10)	POD1, 2, and 3
Length of hospital stay	Day from surgery to discharge	At discharge
Operative time	Minutes (skin incision to wound closure)	Intraoperative
Major complications	Clavien-Dindo classification	Within 30 days
Cost effectiveness	Dressing supply cost, dressing service cost, Dressing frequency	Until discharge
Patient satisfaction and wound quality	Validated wound questionnaire, investigator wound assessment	1 week postop discharge OPD visit

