### **3.8 Sample size calculation**

Sample size was calculated in consultation with the department of Biostatistics, Seoul St. Mary's Hospital. The reference SSI rate following skin stapling in laparoscopic colorectal surgery was estimated at 5.8%, based on published literature (Lee CS et al, 2020). The non-inferiority margin was set at 0.99 percentage points (i.e., the absolute difference in SSI rate between the skin adhesive and stapling groups must not exceed 0.99% in favor of stapling for the tissue adhesive to be declared non-inferior).

Using a one-sided Z test (unpooled), one-sided alpha of 0.025, and power of 80%, the required sample size is 152 participants per group, for a total of 304 participants. No adjustment for anticipated dropout has been made because both interventions are applied at the time of surgery; however, a 10% safety margin may be considered at the interim review.

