### 3.9 Statistical Analysis

All analyses will be performed using SPSS version 27.0 (IBM Corp) or R version 4.3 or later. The primary non-inferiority analysis will be conducted on both the per-protocol (PP) population and the intention-to-treat (ITT) population; non-inferiority will be claimed only if both analyses are concordant.

The primary endpoint (SSI rate) will be analyzed using a one-sided Z test for the difference in proportions, with the 95% confidence interval for the difference (skin adhesive minus stapling) reported. Non-inferiority will be concluded if the upper bound of the 95% confidence interval is below the pre-specified non-inferiority margin of 0.99 percentage points.

Continuous secondary endpoints (VAS, length of stay, operative time, cost) will be compared using the Student's t-test or Mann-Whitney U test as appropriate. Categorical variables (complication rates, patient satisfaction categories, pathological stage) will be analyzed using the chi-square test or Fisher's exact test. A two-tailed p-value of <0.05 will be considered statistically significant for all secondary comparisons.

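### Section 3.9 tests patient satisfaction with chi-square or Fisher's exact test; if it has three or more ordered levels, the test stays valid but ignores order and loses power for a consistent shift

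*Protocol*

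**What the plan says.** Protocol section 2.2 lists as a secondary objective: "To assess wound healing quality and patient satisfaction via a validated questionnaire administered at the outpatient clinic visit one week after discharge". The table in section 3.6.2 gives the tool as "Validated wound questionnaire, investigator wound assessment". Neither place names the instrument, says how many answer levels it has, or says whether the answers are summed, graded or reduced to two groups.

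Section 3.9 then fixes the test: "Categorical variables (complication rates, patient satisfaction categories, pathological stage) will be analyzed using the chi-square test", or Fisher's exact test. The significance rule is "A two-tailed p-value of <0.05 will be considered statistically significant for all secondary comparisons". A rank test appears in the same paragraph for other endpoints only: "Continuous secondary endpoints (VAS, length of stay, operative time, cost) will be compared using the Student's t-test or Mann-Whitney U test as appropriate". Section 3.9 names no test for wound quality.

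**The concern.** Satisfaction normally runs from worse to better. Pearson's chi-square, and Fisher's test in its usual form for more than two levels, give the same p-value however the levels are rearranged. A table in which every adhesive patient moves up a step and a table with the same pairs of counts shuffled across levels cannot be told apart. With k levels, the evidence for a consistent shift is spread over k - 1 degrees of freedom, where a rank test concentrates it on one.

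At stake is the sensitivity and readability of one secondary comparison. A real, consistent difference in satisfaction could be missed, and a significant p-value would not by itself carry a direction. Because the protocol names the test, this is a stated choice and not a detail left open for a later analysis plan.

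**Working it through.** **Inputs from the protocol.** 152 per arm (section 3.8: "the required sample size is 152 participants per group, for a total of 304 participants"); allocation 1:1 (section 3.4); two-sided 0.05 for secondary comparisons (section 3.9).

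**Inputs that must be assumed.** Number of levels, control-arm distribution and size of the shift. The protocol gives none of these, so a range is shown.

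**Step 1. The plan's own figure.** The only sample size in the protocol is for surgical site infection. With one-sided 0.025, 80% power, rates 0.058 and 0.010, and margin 0.0099:

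n = (1.960 + 0.842)² × (0.058 × 0.942 + 0.010 × 0.990) / (0.0099 + 0.048)² = 7.849 × 0.064536 / 0.003352 = 151.1, rounded up to 152 per arm.

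Power at 152 is 0.8023, as printed in section 3.8. The protocol makes no power statement for satisfaction.

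**Step 2. One case by hand.** Assume five levels with 20% of control patients in each, and a common odds ratio of 1.7. Dividing each control cumulative odds (0.25, 0.667, 1.5, 4) by 1.7 gives cumulative shares 12.8%, 28.2%, 46.9% and 70.2%. The shifted arm therefore has 12.8 / 15.3 / 18.7 / 23.3 / 29.8%.

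Noncentrality = 152 × Σ (p - q)² / (p + q) = 6.71.

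- On 4 df (critical value 9.488) power is 52.0%.
- The same noncentrality on 1 df (critical value 3.841) gives 73.6%.

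Simulation of this case with 40,000 runs gave 51.6% for chi-square and 73.8% for the tie-corrected Mann-Whitney test.

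**Step 3. Range over scales.** Same simulation, proportional-odds shift, odds ratios 1.5 to 2.0:

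| Levels | Loss of chi-square against Mann-Whitney (percentage points) | Example (chi-square vs Mann-Whitney) |
|---|---|---|
| 2 | none (differences under 0.5) | OR 1.7, even: 63.1% vs 62.7% |
| 3 | 6.5 to 10.9 | OR 1.7, skewed: 49.0% vs 59.9% |
| 4 | 12.9 to 17.4 | OR 1.7, skewed: 50.2% vs 67.6% |
| 5 | 14.3 to 23.0 | OR 1.8, very skewed: 46.0% vs 69.0% |
| 7 | 20.8 to 29.6 | OR 1.7, even: 45.0% vs 74.6% |

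A separate simulation gave about 7 to 10 points with three levels, 12 to 16 with four and 15 to 22 with five. Outside this range of effects the loss is smaller: with five levels, about 9 to 10.5 points at odds ratio 1.3 and 3 to 11 at 2.5.

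**Step 4. Cross-check without simulation.** Take the noncentrality that gives 80% power on 1 df, 7.849. On 2, 3 and 4 df it gives 70.9%, 64.5% and 59.5%, which are losses of 9.1, 15.5 and 20.5 points for three, four and five levels. This agrees with step 3.

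**Step 5. Validity.** Under no difference, chi-square rejected in 4.4% to 5.0% of runs. The test is not invalid.

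**Step 6. Where the ranking reverses.** With five levels, control shares 20% each and the other arm 28 / 15 / 14 / 15 / 28%, chi-square has about 60% power and Mann-Whitney about 5%. A rank test does not see a difference that has no overall direction.

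**The case against.** Four objections deserve an answer.

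- **The order of the scale is inferred.** The protocol never says that satisfaction has several ordered levels. Satisfied against not satisfied would fit its wording, and chi-square would then be suitable. This stands, and it is why the point is conditional.
- **The simulations favour the rank test.** They assume a consistent shift, and step 6 shows the opposite result for a non-monotone difference. Such a pattern is conceivable: section 5.1 lists allergic or contact dermatitis as a possible event with adhesive, so a dissatisfied minority could sit beside a satisfied majority. This also stands. It is a reason to show the category percentages, but not a reason to ignore order in the test.
- **Direction is visible anyway.** Percentages by arm usually accompany a chi-square test, and section 2.2 says assess for this objective where the other secondary objectives say compare. That softens the point about direction. Still, section 3.9 does list satisfaction for testing and sets a threshold for it, and the lost power is not recovered by reading a table.
- **Pathological stage is ordered too.** True, but it is not listed as an endpoint in section 3.6.2, so little depends on its test.

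A reader might infer that the trial as planned certainly loses some 15 to 23 points of power on satisfaction. The protocol does not support that: the figure needs about four or five ordered levels and a moderate shift, none of which it states. Nor does it support saying that wound quality is tested wrongly, because section 3.9 gives no test for it.

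**Conclusion.** The point holds conditionally. Section 3.9 fixes an order-blind test for satisfaction without saying what the levels are. If there are three or more ordered levels, the test remains valid but gives up power for a consistent shift: roughly 7 to 11 percentage points with three levels and 12 to 23 with four or five. With two levels nothing is lost. These figures rest on 152 analysed per arm, odds ratios of 1.5 to 2.0, a proportional-odds shift and assumed control distributions. This is lost efficiency on one secondary endpoint, worth correcting because the correction is nearly free. The non-inferiority conclusion on surgical site infection does not depend on it.

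**What to change.** In section 3.9:

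- Name the questionnaire, give its answer levels and state which end is better.
- For satisfaction, and any wound-quality rating, recorded in three or more ordered levels, use the Wilcoxon-Mann-Whitney test or a proportional-odds model.
- Report a directional effect with its 95% CI: the probability of a better score, or a common odds ratio.
- Keep chi-square or Fisher's exact test for binary and nominal variables such as complication rates.
- Tabulate category percentages by arm so that a non-monotone pattern stays visible.

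The cost is a sentence or two and no new data. The one downside is less sensitivity to differences without a direction. The change should be made before outcome data are analysed, so that the choice of test cannot follow the results.

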## 4. Study Schedule

		Study Period						
		Enrollment	Allocation	Post-allocation				Close-out
	Time point	-2 to 0 day	Operation day	Postoperative day 1	Postoperative day 2	Postoperative day 3	Discharge	First OPD f/u
Enrollment	Eligibility screen	O						
	Informed consent	O						
	Randomization		O					
	Allocation		O					
Intervention	Experimental intervention		O					
	Control intervention		O					
Assessment	Demographical data	O						
	Medical history	O						
	Laboratory	O	O		O		O	
	Parameters of surgical procedure		O					
	VAS score		O	O	O	O		
	Documentation of SSI		O	O	O	O		O
	Documentation of other complication		O	O	O	O		O
	Length of hospital stay							O
	readmission							O
	Patient questionnaire							O
	Pathologic results							O
	Cost outcomes							O

## 5. Safety considerations

### 5.1 Anticipated Adverse Events

Both study interventions represent standard of care wound closure modalities routinely used in clinical practice. No additional risk is introduced beyond routine postoperative wound complications. Anticipated adverse events include:

- Wound dehiscence

- SSI (Superficial or deep incisional)
- Allergic or contact dermatitis (potential for tissue adhesive group)
- Staple-site pain or hypersensitivity (skin stapling group)

## 5.2 Stopping Rules and Withdrawal Criteria

An individual participant will be withdrawn from the study if:

- The participant withdraws consent at any time
- The participant receives wound-healing-modifying medications (immune-suppressants or systemic corticosteroids) not present at baseline
- The participant undergoes an unplanned additional abdominal surgery within the observation period

There are no predefined stopping rules for the overall trial, as both interventions carry minimal incremental risk beyond standard care.

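### Section 5.2 withdraws patients from the study for reoperation or new steroids/immunosuppressants, which puts outcome-related 30-day data at risk and conflicts with Sections 3.8, 3.9 and 5.3

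*Protocol*

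**What the plan says.** Section 5.2 opens its list with "An individual participant will be withdrawn from the study if" and then gives three triggers. One is withdrawal of consent. The other two are clinical events after randomisation:

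- "The participant receives wound-healing-modifying medications (immune-suppressants or systemic corticosteroids) not present at baseline"
- "The participant undergoes an unplanned additional abdominal surgery within the observation period"

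Other parts of the protocol assume complete 30-day data:

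- **Section 3.9:** "The primary non-inferiority analysis will be conducted on both the per-protocol (PP) population and the intention-to-treat (ITT) population", and "non-inferiority will be claimed only if both analyses are concordant". Neither population is defined in the protocol.
- **Section 3.6.1:** the primary endpoint is superficial or deep incisional SSI within 30 days of surgery.
- **Section 2.2:** "To compare the incidence of major postoperative complications within 30 days". The table in Section 3.6.2 has these graded by Clavien-Dindo.
- **Section 5.3:** all adverse events are recorded from randomisation to the 30-day visit, with no exception for withdrawn patients.
- **Section 3.8:** no dropout allowance is made, because both closures are applied at the operation.

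**The concern.** The wording is withdrawal from the study, not from a treatment or from the PP set. Closure is finished at the end of the operation, and Section 3.8 relies on that fact. The rule therefore has nothing to act on except data collection or analysis.

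The triggers are not neutral. An unplanned abdominal reoperation is itself a postoperative complication of the kind the secondary endpoint counts, and it may follow from a wound problem. Section 5.1 lists dehiscence and SSI among the anticipated events. New systemic corticosteroids could also differ by arm, since Section 5.1 lists "Allergic or contact dermatitis (potential for tissue adhesive group" for the adhesive arm only.

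Loss that is related to outcome, and possibly to arm, could affect the ITT and PP analyses alike. Requiring the two to agree would then give no protection against it. An SAP can define the populations, but it cannot recover outcomes that were never collected.

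**Working it through.** **1. The plan's own figure.** Inputs from Section 3.8 and its software output: adhesive rate p1 = 0.010, stapler rate p2 = 0.058, margin 0.0099, one-sided alpha 0.025, power 80%, unpooled Z test.

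n = [p1(1−p1) + p2(1−p2)] × (1.960 + 0.842)² / (margin − (p1 − p2))²

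= 0.064536 × 7.849 / 0.0579² = 151.1, rounded up to **152 per arm**.

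Power at 152 per arm is Φ(0.0579/0.02061 − 1.960) = Φ(0.850) = **0.802**. Both stated figures reproduce.

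**2. Expected events.** Adhesive: 152 × 0.010 = 1.5. Stapler: 152 × 0.058 = 8.8. Total: about 10.3 SSIs.

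**3. Power if withdrawn patients leave the analysis.** The protocol gives no withdrawal rate, so these rates are assumptions.

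| Withdrawn per arm | Analysed per arm | Power |
|---|---|---|
| 0% | 152 | 80.2% |
| 2% | 149 | 79.4% |
| 5% | 144 | 78.1% |
| 10% | 137 | 76.0% |

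**4. Sensitivity to single lost cases.** Upper 95% bound = (a − b) + 1.96 × √[a(1−a)/n1 + b(1−b)/n2], where a and b are the observed adhesive and stapler rates. Non-inferiority needs a bound below +0.99 points.

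| Adhesive | Stapler | Difference | Upper bound | Result |
|---|---|---|---|---|
| 4/152 | 9/152 | −3.29 | +1.24 | fails |
| 3/151 (one adhesive SSI lost) | 9/152 | −3.93 | +0.43 | passes |
| 3/152 | 9/152 | −3.95 | +0.41 | passes |
| 3/152 | 7/150 (two stapler SSIs lost) | −2.69 | +1.34 | fails |

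The first pair shows lost cases creating a non-inferiority claim. The second pair shows them destroying one.

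**5. How typical this is.** Under the planning rates, 4 or more adhesive SSIs in 152 has a binomial probability of about 7%. Summed over all outcomes at those rates, losing one adhesive SSI turns a fail into a pass about 8% of the time. Larger counts can survive a loss: 5/152 v 9/152 fails at +2.07, and 4/151 v 9/152 still fails at +1.27.

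**6. The rules side by side.** Section 5.2 ends participation at the trigger. Section 5.3 continues adverse event recording to day 30. Section 3.9 needs an ITT analysis of a 30-day outcome. No section says whether a withdrawn patient is followed further or stays in ITT.

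**The case against.** The strongest reply is that Section 5.2 never says withdrawn patients leave the analysis or that their data are discarded. An ITT set can keep them as randomised with partial or missing outcomes, and an SAP that is not shown may say so. Section 5.3 can be read as continuing SSI capture, because Section 5.1 lists SSI as an anticipated adverse event. The reoperation is the trigger, so it is known at withdrawal and can be counted.

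This reply is right against two stronger readings that a reader might infer:

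- **The ITT analysis is not ITT.** The documents do not support this, because no section removes these patients from the ITT set.
- **Reoperations necessarily vanish from the major-complication endpoint.** Stopping data collection after the trigger does not erase the trigger. The reoperation is lost only if withdrawn patients are dropped from the analysis, which the protocol does not state.

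Three further limits stand. The 4-versus-3 example sits at the edge of the decision rule, and no direction of bias is shown. Nothing in the protocol shows that reoperated patients would be SSI cases. The route from dermatitis to systemic steroids is only a possibility, since Section 5.1 calls the dermatitis potential and says nothing about its treatment.

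What the reply does not remove is the conflict. If Section 5.3 is read as overriding 5.2, the withdrawal has little left to do. If 5.2 is applied as written, outcomes after the trigger may go uncollected. A later definition of analysis sets cannot settle which patients are followed.

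**Conclusion.** The point holds as a conflict between a stated withdrawal rule and the rest of the protocol. SSI and complications after the withdrawal date are at risk of being lost for patients whose trigger may be linked to outcome. The triggering reoperation is also at risk if withdrawn patients are left out of the analysis.

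The main issue is selective loss, not power. At an assumed 5% withdrawal, power falls only from 80.2% to 78.1%. With about 10 SSIs expected, one or two selectively lost cases can change the conclusion in either direction, though they would do so in a minority of outcomes under the planning rates.

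This rests on three assumptions: the observation period, which the protocol does not define, is the 30 days of the primary endpoint; withdrawal rates are in the range shown; and the interval is the unpooled Wald form that matches the sample size calculation. The matter touches the primary analysis and should be settled in the protocol.

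**What to change.** Reconcile Section 5.2 with Sections 3.9 and 5.3 by stating that:

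- only withdrawal of consent ends data collection;
- after an unplanned abdominal reoperation, or new immunosuppressant or systemic corticosteroid use, the participant stays in follow-up to day 30 and in the ITT and complication analyses;
- such an event bears only on PP membership, or on a sensitivity analysis;
- the number of such events is reported by arm.

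This concerns data retention and analysis, not clinical care. It would also make the reason given in Section 3.8 for no dropout allowance consistent with Section 5.2. If withdrawn patients were to be left out instead, keeping 152 evaluable per arm would need 152/0.95 = 160 per arm at an assumed 5%.

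The cost is a few lines of protocol text and the follow-up of a small number of patients, for whom Section 5.3 already requires adverse event recording to day 30.

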## 5.3. Adverse Event Reporting

All adverse events will be recorded from the time of randomization through the 30-day follow-up visit. Serious adverse events (SAEs) will be reported to the IRB within 24 hours of the investigator's awareness and managed according to institutional and national regulatory guidelines.

